2.5.2. Subject Discontinuation

Subjects will participate in the study until they complete the 6-months post treatment assessments. Subjects who do not complete the study per protocol may be exited from the study in the following manner:

Subject Voluntary Withdrawal

Subjects may withdraw their consent and discontinue participation in the study at any time for any reason or no reason, without jeopardizing their medical care. If a subject withdraws consent then it will be documented on the study exit form, and the reason for withdrawal will be requested.

Investigators must also report this to their respective Ethics Committee (EC) as defined by their institution's procedure and local EC requirements. No additional follow-up will be required and no additional data will be recorded from subjects once a subject has withdrawn from the trial. Subjects will not be replaced.

Subject Lost-to-Follow-up

In the event a subject cannot be contacted for post-treatment assessments, at least three attempts should be made to locate the subject and these efforts will be documented. Subjects will be

discontinued from the study if they are lost to follow-up. It should be understood that more than three attempts can be made, but three is the minimum required.

Investigator Withdrawal

Subjects may be withdrawn by the investigator prior to receiving an injection if, on the day of injection, it is determined by the investigator that the subject is no longer an appropriate candidate for injection (e.g., due to development of infection of the index joint) then the subject will be withdrawn from the study and will not receive the injection.

Subjects who are withdrawn from the study prior to receiving the index injection will be replaced. The investigator may decide to withdraw the patient from the study at any time based on medical judgment. In all instances of withdrawal, data collected up to the time of patient withdrawal may be used in the study. The site should complete a study exit form.

Endpoint Reached

Subjects who are not satisfied with the improvements in pain, function or stiffness following OOT or splinting treatment in the index thumb joint within 6 months and choose to seek additional treatment for their index trapezio-metacarpal OA will be discontinued from the study.

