2.4.6. Follow-up Visits

Follow-up assessment visits will be at the following intervals following the injection:

1 Month (\pm 7 days)

3 Month (\pm 7 days)

6 Month (\pm 7 days)

The following assessments and information will be collected at follow-up visits:

- DASH (all follow-up visits)
- VAS (all follow-up visits)
- Grip strength test (all follow-up visits)
- Tip pinch strength (all follow-up visits)
- Kapandji score (all follow-up visits)
- Nine-hole Peg test (all follow-up visits)
- Medication use (During the first 6-Month follow-up period, information on all medication usage will be collected)
- AEs (During the first 6-Month follow-up period, all AEs have to be reported.)

The study follow-up visits consist of a structured telephone interview and electronic self-report. The investigative center will contact the subject to complete the Follow-up, Adjunct Therapies and AE forms remotely.

Use of certain pain medication must be discontinued 48 hours prior to assessments (with the exception of aspirin taken for cardio protection). Aspirin in low dose would not be enough to affect any pain sensations. In addition, the low dose aspirin is supposed to be taken every day when taken for cardio-protection, so they should remain consistent on their regimen throughout the study. **In case of pain, it's possible to take Paracetamol 1000 mg 1 tablet (maximum dose 2 tablets per day).**

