2.5.3. Trial Completion

A study exit form must be completed when:

- The subject withdraws from the clinical trial
- The subject is considered lost-to-follow-up per the above definition
- The subject did not receive the index treatment due to disqualifying factors
- The investigator withdraws the subject
- Subject receives additional treatment for index thumb OA within 6 months.
- More than one cross-over of study treatment in index hand
- Subject receives invasive treatment for thumb OA other than one of the study treatments in index hand
- Upon trial follow-up completion (6-months follow-up time point has been reached)
- The subject has died

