7.2. Efficacy Analysis

Data were described as number and percentage, if categorical, or mean and standard deviation, if continuous, unless otherwise specified. Differences were described as mean, standard deviation and 95% confidence interval. Baseline characteristics were presented for the whole sample, while test values over time were presented only for patients who weren't lost to follow up.

Differences between groups were explored with chi square test, with Fisher correction if necessary, for categorical variables, or with Student t-test for continuous variables approximately Gaussian, or with Mann Whitney test otherwise. Adherence to Gaussian distribution were verified with Shapiro Wilks test.

About primary outcome, DASH and NRS were also described as percentage of patients reaching the minimal importance difference of 10.83 and 2 points, respectively.

Significance threshold was set to 0.05, all analyses were made with Stata version 18.

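### Section 7.2 leaves patients lost to follow-up out of the results over time, and section 2.5.2 does not say when a patient counts as lost

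*Combined protocol and SAP*

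**What the plan says.** **Analysis.** Section 7.2 describes baseline for the whole sample, but "test values over time were presented only for patients who weren't lost to follow up". The paragraph on group comparisons that follows does not say which patients enter at each visit, and the section names no method for missing data. Section 7 promises a complete SAP before database lock; the combined document contains only the summary.

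**Follow-up.** Section 2.4.6 schedules the DASH at Months 1, 3 and 6, each within 7 days either side, with follow-up by telephone interview and electronic self-report. Section 2.5.2 opens with "Subjects will participate in the study until they complete the 6-months post treatment assessments".

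**Loss to follow-up.** Section 2.5.2 says "In the event a subject cannot be contacted for post-treatment assessments, at least three attempts should be made to locate the subject", asks that the efforts be documented, and adds "It should be understood that more than three attempts can be made, but three is the minimum required". Patients are to be "discontinued from the study if they are lost to follow-up". Section 2.5.3 then requires an exit form when "The subject is considered lost-to-follow-up per the above definition".

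**Data already collected.** Also in section 2.5.2, under investigator withdrawal: "In all instances of withdrawal, data collected up to the time of patient withdrawal may be used in the study".

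**Sample size.** Section 7.1 needs 16 per group for a 1 SD difference in DASH (80% power, two-sided 5%) and raises this to about 20 to cover losses and other variances. Under section 4.4.1, only randomised subjects who received no treatment fall outside the count.

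**The concern.** There are two separate problems.

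The first is in the analysis. A patient seen at Months 1 and 3 and lost before Month 6 has contributed two DASH scores. Section 7.2, read plainly, shows neither. The group that remains at each visit is then chosen by what happened afterwards. If loss is related to outcome or arm, the comparison shifts; if it is not, precision is still given away.

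The second is in data collection. Section 2.5.3 relies on a definition of loss to follow-up, but section 2.5.2 supplies only a minimum effort: no visit, no deadline, no number of missed visits. The consequence is nevertheless fixed, and no return is described. One site could make three calls in the Month 1 window, exit the patient and comply. Another could try again at Month 3 and also comply. The same patient would yield different data, and at the first site the Month 3 and Month 6 DASH would never be sought even though consent stands. Treated patients who are lost are not replaced, so each exit comes out of the margin built into section 7.1.

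**Working it through.** **1. The plan's own figure.** Inputs from section 7.1: difference 1 SD, two-sided 5%, 80% power, two equal groups. Normal approximation: n = 2(1.960 + 0.842)² / 1² = 15.7, so 16 per group, with power 80.7%. The exact t calculation gives 17 for 80% and 78.1% at 16. The stated 16 reproduces. Since 16 / (1 − 0.20) = 20, the margin is 20 − 16 = 4 per arm, a 20% loss allowance.

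**2. What one exit costs.** Exact t power at 1 SD uses n1 + n2 − 2 degrees of freedom and noncentrality 1/√(1/n1 + 1/n2):
- 20 against 20: 86.9%
- 19 against 20: 86.0%
- 16 against 20 (all four spare places gone in one arm): 82.5%

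**3. Month 6 under two readings of section 2.5.2.** The documents give no probability m of being unreachable at a visit, so m is assumed, equal at the three visits and independent between them. If the first miss means exit, expected Month 6 patients per arm are 20(1 − m)³. If every visit is attempted regardless, they are 20(1 − m). Power is evaluated at the expected number.

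| m per visit | Lost by Month 6, 1 − (1 − m)³ | Exit at first miss: n per arm, power | Every visit attempted: n per arm, power |
|---|---|---|---|
| 2% | 5.9% | 18.8, 84.7% | 19.6, 86.2% |
| 5% | 14.3% | 17.1, 81.1% | 19.0, 85.1% |
| 10% | 27.1% | 14.6, 74.0% | 18.0, 83.0% |
| 20% | 48.8% | 10.2, 57.3% | 16.0, 78.1% |

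Expected loss reaches the 20% allowance when (1 − m)³ = 0.80, so m = 1 − 0.80^(1/3) = 7.2%.

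**4. Sensitivity to independence.** If the same patients are unreachable at every visit, both readings leave 20(1 − m) and the gap disappears. Independence is therefore the unfavourable end of the range from independent to perfectly clustered misses.

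**5. What section 7.2 leaves out.** Under exit at first miss, 20(1 − m) scores per arm are collected at Month 1 and 20(1 − m)² at Month 3, but the plain reading shows only the 20(1 − m)³ patients never lost.

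| m per visit | Month 1: collected, shown, omitted | Month 3: collected, shown, omitted |
|---|---|---|
| 2% | 19.6, 18.8, 0.8 | 19.2, 18.8, 0.4 |
| 5% | 19.0, 17.1, 1.9 | 18.1, 17.1, 0.9 |
| 10% | 18.0, 14.6, 3.4 | 16.2, 14.6, 1.6 |

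The omission itself does not need the exit-at-first-miss reading. It affects any patient with an early score who is later declared lost.

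**The case against.** A reader might infer that one missed contact forces permanent exit. The text does not say so. Section 2.5.2 speaks of assessments in the plural, sets no trigger at a single visit, treats three attempts as a floor, and expects participation through Month 6. Nothing tells a site to stop after Month 1. This stands: early exit is permitted, not required.

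A reader might also infer that one such exit uses up the loss allowance. It takes one of four places in that arm and moves power from 86.9% to 86.0%.

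The 74% against 83% contrast rests on a 10% miss rate that nothing in the documents supports. Here a miss means failing at least three attempts by telephone or electronic contact. At 5% the harsher reading still leaves 17.1 per arm, above 16. The plan also names no primary DASH visit; at 10% missed, Month 3 still has 16.2 scores collected per arm. This stands too, so the figures can only be given as a conditional range.

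On section 7.2, the sentence could mean patients not lost by the visit in question, and it speaks of presentation rather than testing. That reading is possible but not written, and nothing else in section 7.2 says that earlier scores are kept. The statement in section 2.5.2 on using data collected before exit gives limited help: it is permissive, concerns withdrawal, and sits under a different heading from loss to follow-up. The promised full SAP may settle the matter, but the text available does not.

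**Conclusion.** The point holds as a gap in the rules for follow-up and analysis. On its plain reading, section 7.2 is a completer-only rule that sets aside Month 1 and Month 3 DASH scores from patients lost later, with no stated method to recover them. Section 2.5.2 attaches a mandatory and apparently irreversible consequence to a status whose timing it does not define, so sites may exit patients early and forgo later scores.

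The size is conditional. With independent misses and exit at the first one, the Month 6 power cost for 1 SD is about 1.5 percentage points at 2% missed per visit (86.2 − 84.7), 4 at 5% (85.1 − 81.1) and 9 at 10% (83.0 − 74.0). Expected loss exceeds the 20% allowance only above about 7% per visit, and clustering of misses within patients narrows the gap. The documents do not show that loss would differ by arm or outcome, so no direction of bias can be claimed. Nor do they support reading the plan as forcing exit after one miss or as exhausting its margin with one patient.

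**What to change.** **Section 7.2.** State that each visit is presented and analysed for all patients with a value at that visit, including those lost later, with the number per arm shown.

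**Section 2.5.2.** State that a patient not reached after at least three documented attempts within a visit window is recorded as having missed that visit and is contacted again at each later scheduled visit unless consent has been withdrawn. Declare loss to follow-up only once the Month 6 window has closed without contact.

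**Section 2.5.3.** Align the exit-form condition with that definition.

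The cost is a few sentences, a few extra calls for each patient who misses a visit, and denominators that vary by visit. No new procedure is needed.

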1.7. Study Objectives

The primary study objective is to determine whether two injections of OO and thumb splint are superior to the use of only the joint splinting in reducing pain.

1) The primary study endpoint is to establish the improvement in DASH score from baseline.

2) Secondary objectives of this study are:

- Improvement in VAS Pain,
- Improvement in Grip Strength Function,
- Improvement in Tip Pinch Function.
- Improvement in the Kapandji Score.
- Improvement in the Nine-Hole Peg Test.

2. Investigational Plan

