2.6.6.3. Protocol Deviation Form

This form will document deviations from the study protocol.

3. Adverse Event reporting and management

All AEs reported to or identified by investigative center personnel occurring during the study period and after the treatment procedure will be documented. AEs will have the onset and resolution date(s) listed (when known), will have their management and outcome documented (where feasible), and will be assessed for severity, relatedness, and whether they were anticipated. SAEs will be described in a narrative in the final study report.

Anticipated AEs associated with the injection procedure include worsening of hand pain and/or function, effusion, and infection.

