3.3. Reporting Procedures

3.3.1. Adverse Event Reporting

Index Procedure and during 6-month Follow-up

All AEs that occur either during the injection procedure or during the 6-month follow-up phase of the study will be documented as described above as soon as possible upon knowledge of the event.

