7.5. Safety Analysis

The safety profile of OOT will be characterized by summarizing AEs, which will be standardized using the Medical Dictionary for Regulatory Activities. Characterization will include narratives of all SAEs and descriptive statistics including AE incidence overall and per subject, AE severity, AE device relatedness, and AE onset for each treatment group. AEs will also be used to characterize the safety of a repeat OOT injection. Results will be tabulated by treatment group.

8. Study monitoring and quality control

The investigational sites will be monitored to ensure compliance with the trial protocol, adherence to applicable regulations, and accuracy of trial data. Monitoring visits will be conducted primarily to ensure that the safety and wellbeing of the subjects is preserved. Monitoring visits will also be used to verify that trial data submitted on case report forms are complete and accurate with respect to the subject medical records and to verify device accountability. The principal investigator, his/her delegate(s) and the study coordinator(s) shall be accessible during monitoring. Accessibility is of particular importance for reviewing data in the CRF. Site personnel will complete CRFs following each subject visit. Trial data submitted will be reviewed against patient charts and other sources containing original patient records. As needed, intermittent monitoring visits will be conducted to compare data entered into the database to a selected sample of the subjects' source documents. Monitoring efforts will be expanded where the sample suggests irregularities.

Prior to the first site activation, a Monitoring Plan will be established outlining the activities above, as well as management of trial materials supplied to sites.

9. Ethical and legal considerations

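### Section 2.5.2 ties a withheld injection to leaving the study, so an ozone patient with a complication after injection 1 can exit before any post-treatment outcome is measured

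*Combined protocol and SAP*

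**What the plan says.** The Investigator Withdrawal paragraph of section 2.5.2 begins: "Subjects may be withdrawn by the investigator prior to receiving an injection if, on the day of injection". The condition is that the investigator no longer considers the patient a suitable candidate, and the example given is "due to development of infection of the index joint". The sentence closes: "then the subject will be withdrawn from the study and will not receive the injection". The next sentence uses a narrower term, and only for replacement: "Subjects who are withdrawn from the study prior to receiving the index injection will be replaced". The paragraph then adds a general power for the investigator to withdraw any patient at any time on medical judgment, and says that data gathered before withdrawal may be used. Section 2.5.3 requires an exit form when the investigator withdraws a subject.

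Section 1.7 describes the experimental treatment as "two injections of OO and thumb splint", and Appendix A schedules one injection a week for two weeks. The comparator in section 2.4.2 is the splint alone. After baseline, DASH is collected at months 1, 3 and 6 (section 2.4.6, Appendix A).

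On safety, section 3 states: "Anticipated AEs associated with the injection procedure include worsening of hand pain and/or function, effusion, and infection". Section 3.3.1 states: "All AEs that occur either during the injection procedure or during the 6-month follow-up phase of the study will be documented". Section 7.2 presents test values over time only for patients not lost to follow-up and names no method for missing values.

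**The concern.** The rule joins two separate events: a treatment decision (this injection is not given) and a data-collection decision (this patient leaves the study). The first is clinical and belongs to the investigator. The second does not have to follow from it.

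The link matters because the trigger can be a consequence of the treatment under test and exists in one arm only. A patient whose joint reacts badly to the first injection is the patient most likely to be judged unsuitable for the second. If that patient then leaves the study, a poor early course drops out of the ozone results while a comparable course in the splint arm meets no equivalent trigger. At stake are the fairness of the DASH and VAS comparison and the record of how local complications of the injection develop.

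**Working it through.** **1. The passages set against the calendar.**
- Day of injection 1: ozone arm only.
- About one week later, day of injection 2: ozone arm only. Section 2.5.2 speaks of an injection, not the first one, so its trigger can operate on this day. Infection is both the rule's own example and an anticipated event in section 3.
- Month 1, with a window of 7 days either side: first post-baseline DASH and VAS in both arms.

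A patient withdrawn on the day of injection 2 therefore has a baseline DASH but no post-treatment value. Section 7.2 compares those with values, so the patient contributes nothing to the primary comparison.

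**2. The planned sample size (section 7.1).** Inputs: difference 1 SD, two-sided 5%, power 80%.

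n per group = 2 × (1.960 + 0.842)² / 1² = 15.7, rounded up to 16. This reproduces the stated figure. Enrolling 20 corresponds to 16 / (1 − 0.20) = 20, an allowance of 4 losses per arm.

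**3. Is power the problem?** Noncentral t power for 1 SD, with 20 splint patients and 20 − k ozone patients:
- k = 0: 86.9%
- k = 1: 86.0%
- k = 2: 85.0%
- k = 3: 83.8%

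Power stays above 80%, so any harm comes through bias.

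**4. Size of the bias.** Neither input is in the documents. Assumptions: k of 20 ozone patients are withdrawn between injections (k = 0 to 3), and they would have scored D = 1 SD worse on DASH than the ozone patients who remain. Let m be the mean of those who remain; higher DASH is worse.

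Mean of all 20 = [(20 − k) × m + k × (m + D)] / 20 = m + kD/20.

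The completers therefore look better than the randomised arm by kD/20:
- k = 0: 0
- k = 1: 1/20 = 0.05 SD
- k = 2: 2/20 = 0.10 SD
- k = 3: 3/20 = 0.15 SD

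**5. Effect on the test.** If the true difference between the arms as randomised is zero, a bias of this size makes the nominal 5% test reject in about 5.3%, 6.0% and 7.3% of trials for k = 1, 2 and 3 (t approximation, common SD).

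**6. Sensitivity to D.** With D from 0.5 to 1.5 SD and k from 1 to 3, the shift runs from 0.025 to 0.225 SD and the rejection rate from about 5.1% to 10.2%.

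**The case against.** The strongest reply is that the rule is a last eligibility check before treatment starts. It asks whether the patient is still a suitable candidate and is followed at once by replacement before the index injection. Section 2.5.3 has a matching exit reason, and sections 2.4.4 and 2.4.6 are written as if there were one injection. On that reading nobody is removed between injections. This is possible, but the text does not say it and the schedule has two injections. Nor does it clear the rule: an ozone patient already randomised could still be exited and replaced on a trigger the splint arm lacks.

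Several stronger conclusions that a reader might draw are not supported:
- *Withdrawal is automatic.* The sentence opens with a permission and ends with a certainty, so it is internally mixed.
- *Splint patients are sure to be followed to month 6.* The medical-judgment power applies to them too. What they lack is the injection-day trigger.
- *Replacement works in one arm only.* The sentence in 2.5.2 is tied to the injection, but sections 2.5.1 and 4.4.1 give replacement wording that fits both arms.
- *The rule spoils the planned description of repeat-injection safety.* Section 7.5 says "AEs will also be used to characterize the safety of a repeat OOT injection", but a patient whose second injection is withheld has had no repeat injection, in the study or out of it.
- *All later adverse-event data are lost.* The statement that no more data are recorded stands under voluntary withdrawal. For investigator withdrawal the loss is inferred from leaving the study, the exit form and the wording on data already gathered. It is probable, not stated.

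**Conclusion.** The point holds as a defect of wording with a one-sided consequence. Section 2.5.2 provides no route for a patient to miss an injection and remain in follow-up. Read as written, it lets a complication of injection 1 end an ozone patient's participation before any post-treatment DASH, and it sits badly with the six-month adverse-event documentation in section 3.3.1.

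The size is uncertain and probably modest: 0 to 0.15 SD in favour of ozone, against a planned difference of 1 SD, for 0 to 3 of 20 patients with a deficit of 1 SD. Both figures are assumptions, and zero is a real possibility because the window is about one week in 20 patients. The direction depends on withdrawn patients having done worse than those who stay, which is plausible for joint complications but not established by the documents. A reader might infer that the trial's result is materially biased, or that every exit other than withdrawal of consent should be abolished; the evidence supports neither.

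**What to change.** Reconcile section 2.5.2 with sections 1.7 and 3.3.1 and with Appendix A by treating an injection not given and withdrawal from the study as separate events. Wording along these lines would do: if a randomised subject does not receive the first or the second injection, the reason is recorded; unless consent is withdrawn, the subject stays in follow-up, with DASH, VAS, medication use and adverse events collected at months 1, 3 and 6, and is analysed in the arm assigned by randomisation. Resolve the mixed permissive and mandatory wording in the same edit. For a missed first injection, check that the replacement sentence in 2.5.2 and the exclusion of untreated subjects in 2.5.1 agree with the new text.

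Whether and when to inject remains the investigator's decision and is not judged here. The medical-judgment withdrawal and the other exit provisions are outside this point.

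The cost is a protocol amendment and a few extra contacts. Section 2.4.6 already provides for telephone and electronic follow-up, so no additional clinic visits are needed for these items.

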2.6.6.2. Study Exit Form

This form will document termination of each subject's study participation and capture the reason for study exit.

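### Patients who exit because they are dissatisfied have no later DASH or VAS scheduled and no stated place in the analysis; separately, randomised but untreated patients fall outside intent-to-treat

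*Combined protocol and SAP*

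**What the plan says.** **Exit for lack of satisfaction.** Under Endpoint Reached, Section 2.5.2 states that patients who are not satisfied after OOT or splinting within 6 months and "choose to seek additional treatment for their index trapezio-metacarpal OA will be discontinued from the study". Section 2.5.3 requires an exit form when "Subject receives additional treatment for index thumb OA within 6 months", and also lists "More than one cross-over of study treatment in index hand". No cross-over is described elsewhere. Section 2.6.6.2 says of the exit form: "This form will document termination of each subject's study participation and capture the reason for study exit".

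**Scores after exit.** Section 2.4.6 and Appendix A place DASH and VAS at 1, 3 and 6 months. The Study Exit column of Appendix A carries only adverse events and the exit form. An explicit stop to data collection, "no additional data will be recorded from subjects once a subject has withdrawn from the trial", appears only under voluntary withdrawal. Under investigator withdrawal, Section 2.5.2 adds for all withdrawals that "data collected up to the time of patient withdrawal may be used in the study", without saying how.

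**Analysis.** Section 7.2 compares groups by t-test or Mann-Whitney. Its nearest approach to an analysis set is a presentation rule: "test values over time were presented only for patients who weren't lost to follow up". Section 2.5.2 treats loss to follow-up and Endpoint Reached as different categories. Section 1.7 names improvement in DASH as the primary endpoint but gives no time point. Section 7 announces a full SAP before database lock.

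**Untreated patients.** Section 2.5.1 places patients who have a study ID but no treatment outside the intent-to-treat population. Section 4.4.1 says that patients untreated after randomisation do not count toward the sample size. Section 2.5.2 adds: "Subjects who are withdrawn from the study prior to receiving the index injection will be replaced".

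**The concern.** Dissatisfaction with pain and function is close to what VAS and DASH measure, so the exit rule selects on outcome. If no score is taken afterwards and only patients with scores are compared, the groups compared may no longer be the groups that were randomised. Loss of poor responders from the OOT arm moves the estimate towards OOT. Loss from the splint arm moves it against OOT and costs power if OOT works. An analysis method can still be written into the SAP, but missing scores cannot be collected after the fact.

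The handling of untreated patients is a separate matter. It is selection after randomisation, not selection by response. It could act unequally because only one arm waits for an injection.

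**Working it through.** **1. The plan's own figure.** Section 7.1 gives a difference of 1 SD, 80% power and two-sided 5%. Then n = 2(1.960 + 0.842)² / 1² = 15.7, so 16 per group, as stated. The t-based solution is 16.7, so 17. By the t-test, power at 1 SD is 78.1% with 16 per group and 86.9% with 20. The margin is (20 − 16)/20 = 20%, or 4 patients per arm. It protects numbers, not comparability. The sample size is not in dispute.

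**2. Assumptions.** The documents give no exit rates. The scenarios below assume 20 per arm, outcomes with unit SD, a t-test on patients with scores, and an exit signal correlated ρ = 0.5 or 0.7 with outcome. They are not forecasts.

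**3. One common exit rule in both arms.** Patients leave when the signal falls below a cutoff c, set so that 20% of the splint arm leaves (c = −0.842). The mean of those who stay shifts by ρ·φ(c)/(1 − Φ(c)).
- Splint: 0.280/0.800 = 0.350.
- OOT with a true 1 SD effect (cutoff c − ρ): 0.162/0.910 = 0.178 at ρ = 0.5; 0.122/0.938 = 0.130 at ρ = 0.7.
- Estimate: 1 + 0.5(0.178 − 0.350) = 0.914; 1 + 0.7(0.130 − 0.350) = 0.846.

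Simulation gives about 0.91 to 0.84 SD, in agreement to within 0.01, and power of about 77% to 74%. With no true effect the two shifts cancel and error stays at about 5%.

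**4. Exits that differ by arm.** Here the k patients with the worst signal leave an arm. The mean of the worst 4 of 20 is −1.33 SD, so 4 exits from one arm shift the difference by ρ × 1.33 × 4/16 = 0.17 (ρ = 0.5) or 0.23 SD (ρ = 0.7).

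| Exits, no true effect | Two-sided error |
|---|---|
| 4 v 2, either way round | 6% to 8% |
| 4 v 0, either way round (upper case) | 8% to 12% |

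The direction follows the arm that loses more. With a true 1 SD effect and 4 splint-only exits, power is about 69% to 64%, against 82% to 83% if 4 patients leave at random.

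**5. What a later model could rescue.** Assume correlations of 0.5 between baseline and each visit, 0.7 between adjacent visits and 0.6 between Months 1 and 6. Let 4 OOT patients exit after Month 1 on a signal tied to the Month 6 score. With no true effect, the Month 6 shift is 0.17 to 0.23 SD for patients with scores. A likelihood model on pre-exit scores leaves 0.10 to 0.14 SD, about 60%. Collecting all scores leaves 0.00, provided that additional treatment does not change them.

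**6. Untreated patients.** No arithmetic applies. Section 2.5.1 speaks of a study ID and names intent-to-treat; Section 4.4.1 speaks of randomisation and the sample size count. Read together, they leave a randomised but untreated patient out of both. Section 2.4.1.4 places final eligibility confirmation before the injection-visit baseline tests, but Sections 2.4.2 and 4.4.1 do not date randomisation against it. How many patients this affects, and in which arm, cannot be derived.

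**The case against.** **Who exits may be a narrow group.** Section 2.3 allows any medication after Month 1. It closes by allowing concomitant OA medication unless listed, with use reported at each follow-up. Section 2.4.6 has an Adjunct Therapies form. Many patients who take extra OA medication may therefore stay in and keep giving scores. A reader might infer from Section 2.5.3 that all of them must leave; Section 2.3 does not support that. The objection stands as far as it goes, and about 20% exits may be too many. The passages still conflict.

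**Non-collection is inferred.** A reader might infer that the protocol forbids later scores for Endpoint Reached patients. It does not say so; the explicit stop covers voluntary withdrawal only. The exit form is weak evidence, since Section 2.5.3 also requires it at normal completion and at death. What remains is that these patients are discontinued and that no score is scheduled at or after exit.

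**The largest error figures need one-sided exits.** The same rule applies to both arms. At ρ = 0.5, 4 v 3 exits give 5.8% error; at ρ = 0.3, even 4 v 0 gives 6.1%. Removing exactly 4 worst-ranked patients from each arm gives 6% to 7%, but that comes from the fixed count; a common cutoff gives about 5%. This stands. A reader might infer that the trial is biased towards OOT, and the documents do not support that. Differing behaviour by arm is possible because no sham injection is described, but it is not established.

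**The SAP is still to come.** It can supply an analysis set and a missing-data method. It cannot supply scores that were not collected.

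**Conclusion.** The concern holds in this form and should be fixed. Exit under Endpoint Reached is related to outcome, no later DASH or VAS is scheduled, and Section 7.2 does not say how these patients enter the comparison. That collection stops is a reasonable inference, not a stated rule. Nor does Section 7.2 state that these patients are excluded: its presentation rule concerns loss to follow-up.

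Size and direction are unknown. Under the assumptions above, a common exit rule costs power and attenuates a true effect without inflating error. Error rises only modestly when exits differ by arm, and the 4 v 0 figure is an upper case for 4 exits at these correlations. Exits after Month 1 do not affect a Month 1 comparison, and no primary time point is named.

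The intent-to-treat point stands on the text and is not quantified. A reader might infer that it removes mainly OOT patients; the timing of randomisation is not given, so the documents do not show this.

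**What to change.** 1. **Sections 2.5.2 and 2.5.3.** Separate ending study treatment from ending data collection. Keep collecting DASH and VAS at the remaining 1, 3 and 6 month contacts, remotely as Section 2.4.6 and Appendix A allow, unless consent is withdrawn. Record additional treatment as an intercurrent event. Reconcile Section 2.3 with the exit triggers, including the cross-over trigger; which clinical rule applies is for the sponsor.

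2. **Section 7.2.** Analyse all randomised patients as allocated, using all available DASH scores, at one time point named in advance. A baseline-adjusted repeated-measures model is one option. Add a pre-specified not-at-random sensitivity analysis that varies the assumed post-exit outcome by arm over a range. A single analysis that sets DASH to baseline after exit is not enough: with no true effect, 4 OOT-only exits and an assumed mean improvement of 0 to 1 SD, it shifts the difference by +0.10 to −0.13 SD, so it does not bound the bias.

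3. **Sections 2.5.1 and 4.4.1.** Define ITT as all randomised patients. Replacements may be added, but no randomised patient is removed.

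**Cost.** Protocol and SAP wording and a few extra telephone or electronic contacts; no larger sample. The downside is that the primary estimate then includes the effect of other treatments taken, which may move it either way.
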